### *Secondary objectives*

1. To determine the course of the histological findings in the two treatment groups.
2. To determine the course of the balance in the subpopulations of lymphocytes (CXCR3highCD4+/CCR4highCD4+) and regulatory cells (Treg CCR4high) using flow cytometry in samples from peripheral blood and FNAP after withdrawal of steroids in the third month post-transplant versus conventional triple immunosuppression.
3. To analyze and compare the incidence of immunological dysfunction in the two treatment arms, as well as graft and patient survival at one and two years of follow-up.
4. To examine the potential metabolic and cardiovascular benefit of steroid withdrawal in terms of renal function, hypertension, diabetes and hyperlipidemia.
5. To assess the adherence to treatment with immunosuppressors in the two treatment groups and its impact on the generation of DSA.

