## STUDY DESIGN AND DURATION

This was a randomized, open-label clinical trial with two treatment arms and a follow-up of two years in patients who received a first deceased-donor kidney transplant. The combinations of immunosuppressors in the study arms were those approved in the technical documentation and used routinely in clinical practice. This was therefore a phase IV clinical trial in the usual conditions of use. The patient recruitment period was 12 months. The minimum follow-up period was 24 months.

**Inclusion criteria:** a) Both male and female patients, 18 years of age or over with no immunological risk (PRA <25% and absence of DSA) who received a first deceased or living donor kidney transplant. b) Patients who for the first three months post-transplant were receiving tacrolimus plus MPA or MMF and steroids and who had stable plasma levels of tacrolimus. c) Absence of clinical or histological immune dysfunction before randomization. d) Absence of de novo DSA at the time of randomization. e) Patients who wished and were able to give their written informed consent to participate in the study. f) Female patients who agreed to use efficient contraceptive methods during the study.

**Exclusion criteria:** a) Recipients of a multiorgan transplant. b) Retransplants. c) Presence of DSA prior to transplant or at the time of randomization. d) Cold ischemia time >30 hours. e) Patients with serum creatinine levels above 2 mg/dL or proteinuria above 1g/day at the time of randomization. f) Previous episode of severe rejection (II-B-III in the Banff/09 classification) before randomization. g) Presence of subclinical rejection in the protocol biopsy before randomization. h) Patients with BK-polyomavirus nephropathy at the time of randomization. i) Patients with recurrent or de novo glomerulonephritis. j) Patients receiving treatment with immunosuppressive drugs other than those of the clinical trial in question. k) Patients who were positive against the human immunodeficiency virus (HIV) or who had a severe systemic infection and who the investigator deems the need for continued therapy. l) Patients who had had any previous malignant disease during the previous five years, except basal cell or excised squamous cell carcinoma.

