**Treatment schedule:**

**Group A: Tacrolimus** 0.15 mg/Kg/day to maintain levels of 8-12 ng/ml for the first two months.

With effect from the third month tacrolimus 0.1 mg/kg/day to maintain levels of 5-8 ng/ml;

**Mycophenolate mofetil (MMF)** 2 gr/day or mycophenolic acid (MPA) 1440 mg/day for the first two weeks post-transplant. With effect from this point MMF 1-1.5 gr/day or MPA 720-900 mg/day; **Steroids:** 0.5 gr of methyl prednisolone intraoperatively and 125 mg on day 1; prednisone 30 mg for the first two weeks post-transplant, then tapering 5 mg/week to reach the dose of 5 mg/day at the second month post-transplant. After this the same dose of prednisone was continued.

This treatment was maintained throughout the whole study period in Group A.

**Group B:** These patients received the same treatment schedule as those of Group A up to the time of randomization (third month post-transplant). After this they received: **Tacrolimus** 0.1 mg/kg/day to maintain levels of 5-8 ng/ml; **MMF** 1-1.5 g/day or **MPA** 720-900 mg/day; withdrawal of steroids between the third and fourth month post-transplant as per usual practice in the center.

Both treatment groups received pre-operatively tacrolimus 0.12 mg/Kg orally and MMF 1 g. or MPA 720 mg. Both treatment groups could receive induction therapy with anti-CD25 monoclonal antibodies (Basiliximab 20 mg iv on days 0 and 4) or polyclonal antibodies (Thymoglobulin 1 mg/kg/day for 4-7 days) in patients at risk of delayed graft function and delayed introduction of tacrolimus.

**Other treatments:** Cases of acute rejection were treated with 3 boluses of 500 mg/day of i.v. methylprednisolone. Cases of steroid-resistant rejection were treated with a standard cycle of 7-10 days of rabbit thymoglobulin. Cases of acute humoral rejection were treated in accordance with the protocol at each center: plasmapheresis, immunoglobulins, and rituximab, either alone or in combination.

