### **Variables:**

#### *Efficacy variables:*

The *primary variable* was the presence of donor-specific anti-HLA antibodies (DSA) at 24 months.

The *secondary variables* were:

- a) Graft and patient survival.
- b) Rate of acute clinical rejection, confirmed by biopsy, calculated glomerular filtration rate (determined by aMDRD) and proteinuria at 3, 6, 12 and 24 months.
- c) BP figures and number of hypertensive patients, lipid levels and need for lipid-lowering drugs, and increase in weight and BMI.
- d) Rate of post-transplant diabetes mellitus (PTDM) or glucose intolerance one year post-transplant according to the criteria of the ADA (PTDM: baseline glycemia  $\geq 126$ , or  $\geq 200$  mg/dl after glucose overload, or need for treatment; glucose intolerance: glycemia after overload of 140-199 mg/dL).
- e) Determination of the lymphocyte subpopulations (CXCR3highCD4+; CCR4highCD4+ and Treg CCR4high) by flow cytometry at 1, 3, 6, 12, 18 and 24 months.
- f) Appearance of acute or chronic pathological lesions of the graft using:

\*Kidney graft biopsy. Biopsies were done before randomization (month 3 post-transplant) and in month 24 post-randomization (protocol biopsies). In the case of suspected acute rejection a biopsy of the graft was done before or within 48 hours of starting anti-rejection treatment. Likewise, a graft biopsy was done at any time if graft dysfunction was detected, as evidenced by proteinuria 0.5 g/day or an increase in the serum creatinine of 25% above its baseline level. The biopsies were evaluated according to the Banff'09 classification (*Sis B, et al Am J Transplant 2010;10: 464-71*). Biopsies done for clinical indication and those done prior to randomization were evaluated locally at each participating center. The local pathologist interpreted the biopsy for the presence of clinical or subclinical rejection, borderline lesions or progression of chronic lesions that

explained a possible graft failure to thus provide the most opportune treatment. The biopsies done and the pre-randomization and final visits were also sent to the pathologist at Carlos Haya Hospital, Malaga, who also interpreted and classified them using the same Banff'09 criteria. The biopsies were processed in each center and sent to the central pathologist for study. The slides comprised at least 2-3 slices of the biopsy. The staining was done locally (hematoxylin eosin, periodic acid Schiff, Masson trichrome and methenamine silver).

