#### **FNAP for morphological analysis and flow cytometry:**

The FNAP was done according to the technique of Hayry (Kidney Int. 1989;36:130-141) with the same periodicity as that for the DSA and if there was any suspicion of immune dysfunction. Aspirate samples were obtained with a Ham solution (10 ml). With the 0.8 mm / 25G needle implanted in a Cameco-Gun device the cortical region of the graft was punctured with local anesthesia, and aspirating by vacuum about 20  $\mu$ L of cell material in a Hepes buffer culture

medium with heparin and human serum albumin (Ham solution). At the same time, a blood sample was obtained to calculate the corrected index (CI), which was the result of the differential in the leukocyte count between the FNAP specimen and the peripheral blood sample. The numerical differences for each cell subtype were multiplied by a correction factor and the sum of the different corrected increases described the intensity of the inflammation. A CI greater than 3 was considered suggestive of acute rejection. The aspirate was processed by flow cytometry to analyze the lymphocyte subpopulations in the same way as these were analyzed in peripheral blood, described above.

**Other determinations:** The patients were monitored for renal function, levels of calcineurin inhibitors, blood count and other parameters, and imaging tests as per clinical practice in Spain. The concomitant treatment was also as usual. The fasting glucose figures were monitored daily during the first week, at least twice during the second week, and at least weekly until the end of the first month. During the second and third months they were monitored at least once every two weeks. With effect from the third month and until the end of the first year they were monitored at least once a month. The HbA1c was measured and a standard oral glucose tolerance test of 75 gr was done at 3, 12 and 24 months.

**Pregnancy tests:** These tests were done for all women who were potentially considered to be of child-bearing age in phases I (screening) and II (randomization) of the study. The pregnancy tests were done locally in serum using detection of the human chorionic gonadotropin hormone.

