## **STATISTICAL ANALYSIS PLAN.**

Descriptive statistics are presented together with the various analyses. Both an intention-to-treat analysis and an analysis according to the final treatment were done. The categorical variables were analyzed using the chi-square test or Fisher's exact test, according to needs. The quantitative data were analyzed using the Student t test or the Mann-Whitney U test, according to needs. Changes over time in the DSA and lymphocyte subsets in the two study groups were analyzed using a general linear model for repeated measures, adjusting for confounding variables. Correlations between the various subsets were analyzed using Pearson correlation. The graft and patient survival curves were calculated with the Kaplan-Meier method. The rates of survival of the groups were compared with the log-rank test. Finally, a linear regression analysis was done to determine the factors associated with the generation of de novo DSA, including steroid withdrawal. The data were analyzed using SPSS 20.0.

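### HbA1c, eGFR and proteinuria are planned for unadjusted comparison although month-3 values were scheduled at randomisation; the metabolic results also need corrected wording and stated numbers, tests and PTDM counts

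*Combined protocol and SAP*

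**What the plan says.** Secondary objective 4 is "To examine the potential metabolic and cardiovascular benefit of steroid withdrawal in terms of renal function, hypertension, diabetes and hyperlipidemia". Three of the continuous outcomes that serve it have a scheduled month-3 value:

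- Efficacy variables, item b: "calculated glomerular filtration rate (determined by aMDRD) and proteinuria at 3, 6, 12 and 24 months".
- Other determinations (under the FNAP heading): "The HbA1c was measured and a standard oral glucose tolerance test of 75 gr was done at 3, 12 and 24 months".

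The Treatment schedule places randomisation at the third month post-transplant, so these month-3 values belong to the time of randomisation.

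For analysis, the Statistical Analysis Plan states "The quantitative data were analyzed using the Student t test or the Mann-Whitney U test, according to needs". Its adjusted model has a narrower scope: "Changes over time in the DSA and lymphocyte subsets in the two study groups were analyzed using a general linear model for repeated measures". The confounders listed under Efficacy variables do not include the month-3 value of HbA1c, eGFR or proteinuria.

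PTDM is defined as "Rate of post-transplant diabetes mellitus (PTDM) or glucose intolerance one year post-transplant according to the criteria of the ADA". No rule is given for diabetes already present at month 3.

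The Preliminary Results give 52 patients randomised to Group A and 53 to Group B. At the end of follow-up they report:

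- HbA1c 6.3±1.2% vs 5.7±0.6%, p=0.013
- systolic blood pressure 133±16 vs 125±15 mmHg, p=0.055
- proteinuria 209±185 vs 148±82 mg/24h, p=0.303

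PTDM incidence is 25.6% vs 16.7%, p=0.359, with no time point. The first two outcomes are described as having risen significantly in Group A. The Diabetes, Lipid profile, Blood pressure and Renal function sections state no n, analysis set or test.

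**The concern.** There are three linked issues.

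1. A value of the same outcome at randomisation is usually the strongest available predictor of its later value. Leaving it out means objective 4 is answered less precisely than the scheduled data allow, in a trial of only 105 patients.
2. A statement that a value rose needs a starting value, and none is shown. A statement that it rose significantly needs a p value that supports it. Systolic blood pressure has p=0.055.
3. Without an n, an analysis set or a named test, readers cannot tell how many patients each metabolic comparison rests on. They also cannot tell what the PTDM rates count: all diabetes present at a visit, or only diabetes that is new after some starting point.

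**Working it through.** **Precision available from the month-3 value.** With correlation r between the month-3 and final values, adjustment multiplies the standard error of the arm difference by √(1−r²), which is equivalent to multiplying n by 1/(1−r²). The documents give no r, so these values are assumed.

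| r (assumed) | SE multiplier | Equivalent n multiplier |
|---|---|---|
| 0.3 | √0.91 = 0.95 | 1.10 |
| 0.5 | √0.75 = 0.87 | 1.33 |
| 0.7 | √0.51 = 0.71 | 1.96 |

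The exclusion criteria remove "Patients with serum creatinine levels above 2 mg/dL or proteinuria above 1g/day at the time of randomization". That narrows the month-3 range of renal function and proteinuria and tends to lower r, so the renal gain is probably nearer the first row.

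**Systolic blood pressure: can p=0.055 be reproduced?** Inputs are the reported means and SDs, the randomised arms of 52 and 53, and an assumed Student t test on final values.

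- Pooled SD = √[(51×16² + 52×15²)/103] = 15.50.
- SE = 15.50 × √(1/52 + 1/53) = 3.03.
- t = 8/3.03 = 2.64 on 103 df, p=0.0095.
- Least favourable rounding (difference 7; SDs 16.5 and 15.5): SE = 3.12, t = 2.24, p=0.027.

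The stated 0.055 is not reproduced.

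**HbA1c: can p=0.013 be reproduced?** The reported figures at 52/53 give p=0.0016. With least favourable rounding (difference 0.5; SDs 1.25 and 0.65), the Student test gives 0.0113 and the Welch test 0.0123. A printed 0.013 needs at least 0.0125. With the same rounding and 51/53, the Welch test gives 0.0130, so one fewer Group A patient removes the mismatch.

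**PTDM: which denominators are possible?** This check needs no assumption about the test.

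- Group A: 13/52 = 25.0% and 14/52 = 26.9%, so 25.6% cannot be a count out of 52. Over all n up to 52 it fits only 10/39 or 11/43, leaving 13 or 9 randomised patients outside the rate.
- Group B: 8/53 = 15.1% and 9/53 = 17.0%, so 16.7% cannot be a count out of 53. Over all n up to 53 it fits only multiples of 6 (1/6, 2/12, and so on up to 8/48), leaving at least 53−48 = 5 patients outside.
- None of the 2×8 = 16 pairs gives p=0.359 by Pearson chi-square (closest 0.365, for 11/43 vs 5/30), Yates-corrected chi-square or the two-sided Fisher test. A likelihood-ratio chi-square for 11/43 vs 5/30 does give 0.359.

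**Wording.** The Blood pressure section attaches a claim of significance to p=0.055, while the Lipid profile section treats HDL cholesterol at p=0.095 as not significant. The plan states no alpha; 0.05 is assumed here.

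**The case against.** Under randomisation, a comparison of final values is unbiased and its test is valid. These are secondary outcomes, the trial is complete and open-label, and the benefit of adjustment rests on assumed correlations. At r=0.3 the standard error falls by only 5%. The results are headed as preliminary, so missing denominators are a reporting gap. All of this stands. It limits the adjusted analysis to a supplement but does not remove the case for it.

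Four stronger readings are tempting, and the documents do not support them.

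- **A reader might work back from the p values to the number of patients analysed.** This assumes a t test on final values. The plan also allows Mann-Whitney, and the wording about a rise is compatible with a test on change from month 3. Missing patients or a transcription error are further explanations: Group B triglycerides are printed as 76±9.7, the same figures as Group B diastolic pressure. Nor are the mismatches uniform. At 52/53 a t test on creatinine gives p=0.444 against the stated 0.458, while proteinuria gives 0.031 against 0.303. No analysed n should be inferred.
- **A reader might take the PTDM denominators as evidence of improper exclusions.** Smaller denominators are what one would see if patients with earlier diabetes had been properly left out of an incidence. The documents do not say.
- **A reader might conclude that eGFR was compared without adjustment.** The gap is in the plan only; the Renal function section reports creatinine and proteinuria, and no eGFR comparison.
- **A reader might discount the HbA1c difference as not significant.** Its p=0.013 is below 0.05. What lacks support is the description of a rise.

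**Conclusion.** The point holds in a limited form. The plan leaves scheduled month-3 values of HbA1c, eGFR and proteinuria out of the between-arm comparison. The cost is precision, not validity: the standard error could be multiplied by 0.95 to 0.71 for assumed correlations of 0.3 to 0.7, probably near 0.95 for the renal outcomes. The adjusted results themselves cannot be predicted, because no month-3 means or correlations are given.

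The systolic blood pressure statement contradicts its own p value, assuming the conventional 0.05. The description of a rise in HbA1c and systolic pressure is unsupported by the final means shown.

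The PTDM rates do not have all randomised patients as denominators; that follows from the percentages alone. The systolic p value does not fit a t test on final values at 52/53, but the reason cannot be determined. The HbA1c mismatch is too thin to rely on. No claim is made about the direction or size of any change in the PTDM difference.

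**What to change.** **Statistical Analysis Plan.** For HbA1c, eGFR and log-transformed proteinuria, add an ANCOVA or mixed model with the month-3 value as covariate. Label it post hoc. Show it beside the planned tests, with adjusted differences, 95% confidence intervals and n per arm.

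**Results wording.** Remove the claim of significance for systolic blood pressure. For HbA1c and systolic pressure, say that Group A was higher, unless change from a recorded month-3 value is shown. For blood pressure this depends on such a value existing, since no visit schedule is given for it.

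**Reporting.** For each comparison in the Diabetes, Lipid profile, Blood pressure and Renal function sections, state the n per arm, the analysis set, the test, and whether the final value or the change was tested.

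**PTDM.** Give counts, denominators, the time point, the test and the handling of diabetes present at month 3. Add a table of month-3 status by month-12 and month-24 status for all randomised patients, with missing values shown.

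**Cost.** Wording, one count table and one re-analysis of data the protocol scheduled; no new data collection. Because the results are already known, the adjusted analyses are supplementary and cannot replace the planned ones.

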Drugs to treat the most usual infections, like *Pneumocystis jirovecii* or CMV, were used in accordance with the protocol at each center. Dyslipidemia was treated with statins or with ezetimibe in the event of the appearance of adverse events. Fibrates were avoided, except for gemfibrozil, as they are associated with worsening renal function. Hypertension was treated according to the protocol at each center to obtain a target BP of <130/80 mmHg. As beta blockers have been associated with new onset post-transplant diabetes, they were initially avoided unless they were indicated for another condition (ischemic heart disease, arrhythmia, or other) or in patients with refractory hypertension.

**Criteria for withdrawal of subjects from the study:** Any participant could withdraw from the study at any time, withdrawing their consent, with no need to justify their decision. The investigator could also withdraw patients from the study in the event of the appearance of any concomitant disease or adverse event that, in the judgement of the investigator, warranted withdrawing the patient from the study, or if there were violations of the protocol or other reasons. The investigator attempted to follow any patient with an adverse event at the time of withdrawal and provide the appropriate treatment in the event of any problem.

Patients who developed acute humoral or steroid-resistant rejection during the study were treated with the best maintenance immunosuppression in the opinion of the investigator and were withdrawn from the study. This could consist of adding steroids or an anti-mTOR (sirolimus or everolimus). All these patients were followed in the same way as those who remained in the protocol in order to have a more robust intention-to-treat analysis.

If the study medication was interrupted for any reason for more than 21 consecutive days or for more than two periods of 7 days or more the patient was considered to have abandoned the

treatment prematurely and was only included in the intention-to-treat analysis and excluded from the per protocol analysis.

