#### **Monitoring of donor-specific anti-HLA antibodies (DSA):**

Monitoring of DSA was done with the Luminex assay and X-MAP technology. The presence of DSA was determined pre-transplant and in months 3, 6, 12, 18 and 24.

Before transplant the presence of anti-HLA antibodies was determined in all the patients by Luminex Mixed, which detects the presence of antibodies against HLA-class I and class II antigens. In positive cases the specificity of the antibodies was determined by Luminex SA (*single antigen*). Likewise, in patients with a high risk of sensitization (previous pregnancy or transfusion) the Luminex SA was also done, even if they had had a negative Luminex Mixed result. Before transplant a serum sample was taken from each patient and frozen in three aliquots of 0.5 ml in Eppendorf tubes.

If the patients had no anti-HLA antibodies pre-transplant, monitoring for these antibodies was done throughout the study using the Luminex Mixed assay. When this assay was positive for any of the measurements established in the study a Luminex SA was done to detect the specificities. If, on the other hand, a patient had a positive Luminex Mixed pre-transplant only the Luminex SA assay was done at all the successive study visits.

Any determination with a mean fluorescence intensity (MFI)  $>500$  was considered positive. All determinations of DSA were centralized at the immunology laboratory of Carlos Haya hospital, Malaga.

All the samples obtained from the various participating centers for determination of anti-HLA DSA were stored at  $-80^{\circ}$  or  $-40^{\circ}$  C until being sent. During transit the samples were stored in dry ice.

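### The repeated-measures GLM for DSA and lymphocyte subsets has no missing-data rule, so as written the secondary over-time comparison uses complete cases only

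*Combined protocol and SAP*

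**What the plan says.** The Statistical Analysis Plan section gives one sentence to the longitudinal analysis: "Changes over time in the DSA and lymphocyte subsets in the two study groups were analyzed using a general linear model for repeated measures". The sentence ends by saying that the model carries covariates for confounders. The software statement is "The data were analyzed using SPSS 20.0". The procedure options, the visits entered and the handling of missing values are not given. The same section says "Both an intention-to-treat analysis and an analysis according to the final treatment were done".

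For DSA, the monitoring section says "The presence of DSA was determined pre-transplant and in months 3, 6, 12, 18 and 24". For lymphocyte subsets, the efficacy variables list determinations "by flow cytometry at 1, 3, 6, 12, 18 and 24 months", whereas the flow-cytometry section gives them the DSA timetable, which has no month 1. The FNAP section adds graft aspirates on that same timetable.

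The withdrawal criteria keep patients with humoral or steroid-resistant rejection under the same follow-up as everyone else, "in order to have a more robust intention-to-treat analysis". The primary variable "was the presence of donor-specific anti-HLA antibodies (DSA) at 24 months" is a yes/no result at one time point. The plan assigns categorical variables to chi-square or Fisher's exact test.

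**The concern.** A classical repeated-measures GLM takes one outcome vector per patient. A patient with a gap in that vector, or with a missing covariate, leaves the analysis entirely, including the visits that were measured. With four post-randomisation visits, some needing a graft puncture, some gaps are to be expected.

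The analysis at stake is the arm comparison of lymphocyte subsets over time (secondary objective 2) and the sequential description of DSA. Restricting it to complete records can cost precision. It can also bias the comparison if patients who miss visits or leave differ in their earlier values. It is not the set of all randomised patients that the plan says it analyses.

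A second problem sits in the same sentence. If the DSA outcome is positivity (MFI above 500), a Gaussian linear model does not suit it. If the outcome is MFI, the plan does not say so.

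**Working it through.** **No planned figure to reproduce.** The documents give no sample-size calculation, dropout rate or number analysed for this model. The randomised total is consistent: 230 − 125 = 105 = 52 + 53.

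**Complete cases.** Assume month 3 is observed and each later visit is missed independently with probability m. Patients retained = 105 × (1 − m)^4. For example, 105 × 0.95^4 = 85.5 and 105 × 0.80^4 = 43.0.

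**Standard error of the month-24 arm difference.** Unit variance, 52 and 53 patients, visits at months 3, 6, 12, 18 and 24, a common baseline mean and a separate mean per arm and later visit. The correlation parameter is 0.6, exchangeable or AR(1).

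- Complete cases: SE = sqrt[(1 − ρ²)(1/52 + 1/53)/(1 − m)^4], where ρ is the correlation of month 3 with month 24. At m = 5%, exchangeable (ρ = 0.6): sqrt(0.64 × 0.0381/0.8145) = 0.173. AR(1) (ρ = 0.6^4 = 0.130): sqrt(0.983 × 0.0381/0.8145) = 0.214.
- All observed visits: sum X'R⁻¹X over arms and missingness patterns, weighted by expected numbers, invert, and take the month-24 contrast. At m = 5% this gives 0.159 (exchangeable) and 0.197 (AR(1)). Both ratios round to 1.09.

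| m per visit (assumed) | Patients retained of 105 | SE ratio, exchangeable | SE ratio, AR(1) |
|---|---|---|---|
| 5% | 86 | 1.09 | 1.09 |
| 10% | 69 | 1.19 | 1.19 |
| 15% | 55 | 1.30 | 1.31 |
| 20% | 43 | 1.43 | 1.44 |

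If month 3 can also be missed, 105 × (1 − m)^5 gives 81, 62, 47 and 34. Adding month 1 as a sixth visit gives 77, 56, 40 and 28. Month 1 precedes randomisation, however, and its place in the schedule is itself unclear.

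**Pure dropout.** Same set-up, with a total share D leaving, spread evenly over the four later visits, so that 1 − D replaces (1 − m)^4.

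| D by month 24 (assumed) | Patients retained of 105 | SE ratio, exchangeable | SE ratio, AR(1) |
|---|---|---|---|
| 10% | 95 | 1.008 | 1.007 |
| 20% | 84 | 1.016 | 1.014 |
| 30% | 74 | 1.025 | 1.023 |

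The patterns differ for a simple reason. With 20% independent misses, 105 × 0.8 = 84 patients have a month-24 value, but the GLM keeps 43. With dropout, those who left have no month-24 value under either method, and their earlier visits add little.

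**Indirect signs of incomplete data.** The preliminary results correlate the month-3 CCR4highCD4+ subset with month-24 inflammation. From t = |r| × sqrt[(n − 2)/(1 − r²)], r = −0.431 with P = 0.007 implies n = 38, and r = −0.436 with P = 0.007 implies n = 37. The 7.14% rejection rate in Group A fits only 1/14, 2/28 or 3/42, so at most 42 of 52. The systolic pressure result (133 ± 16 vs 125 ± 15, p = 0.055) implies about 29 per arm, or 22 to 40 allowing for rounding. By contrast, Fisher's test on all 52 and 53 gives 0.110, 0.678 and 0.618 for the serious adverse events, against 0.110, 0.677 and 0.618 reported.

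**The case against.** **Reach.** A reader might infer that the model defeats the intention-to-treat aim of the whole trial. The documents do not support that. The primary variable goes to chi-square or Fisher, survival goes to Kaplan-Meier and log-rank, and the safety p-values reproduce on all randomised patients to within 0.001. This objection stands in full.

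**Rejection withdrawals.** A reader might also infer that patients withdrawn for rejection are deleted. The withdrawal criteria say that they stayed under the same follow-up. If that was done, they have their scheduled measurements and remain in the model unless a sample is missing. What is left is missed samples and withdrawals for other reasons, for which less follow-up is promised.

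**Size.** That much of the sample was lost is a third tempting inference. No missing-visit rate is documented, and the precision loss depends on the pattern: appreciable for scattered misses, close to nil for dropout. The implied sample sizes above concern other variables, and the correlations also required a month-24 biopsy. They make complete data hard to assume, but they do not measure the loss in this model.

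**Deletion is inferred.** The plan names neither the procedure options nor an imputation step. The inference follows from the named method in the absence of another rule. A stated rule would settle it.

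**DSA alternatives.** All patients were DSA-negative at randomisation by eligibility, and the preliminary results say that withdrawal did not lead to DSA appearing. With no or few events, a GEE or logistic model may not be estimable. This stands, so a fallback is needed.

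**Consequence.** The preliminary results report no arm-by-time comparison from this model, so no published figure is shown to be wrong.

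**Conclusion.** The concern holds for the secondary over-time comparison of DSA and lymphocyte subsets and no further. As written, that comparison defaults to patients with every included visit and covariate present, which is not the intention-to-treat set the plan describes.

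The size is conditional. The 86 to 43 patients retained and the SE ratio of 1.09 to 1.44 assume independent misses of 5% to 20% at each of four visits and a correlation parameter of 0.6. The ratio of about 1.01 to 1.03 assumes 10% to 30% pure dropout. Both patterns are assumptions, and the truth may be a mixture. Bias arises if leaving depends on earlier values; the documents give nothing from which to estimate its size. The point is worth correcting, but it does not bear on the 24-month DSA result.

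**What to change.** **Lymphocyte subsets.** Replace the GLM with a mixed model for repeated measures fitted by REML: arm, visit, arm-by-visit and an unstructured covariance, using all observed visits of the 105 randomised patients. Report the number contributing per arm and visit, separately for blood and aspirate. List the covariates and say how missing ones are handled, because a mixed model does not recover those. State whether month 1 was scheduled.

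**DSA.** State whether MFI or positivity is modelled. If MFI, say what value a sample takes when it was negative on screening and had no single-antigen test. If positivity, use a binary method for repeated data or for time to first positive result, with exact per-visit or cumulative comparisons as the fallback if events are too few.

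**Missing data.** Write down the rule for this analysis and add one sensitivity analysis for value-dependent leaving.

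**Cost.** Revised wording and a re-run on existing data. SPSS 20 has suitable procedures (MIXED and GENLIN). Results are already known, so the re-run must be labelled post hoc.
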